11.3.2. Efficacy Data

For secondary and exploratory endpoints, binary data will be analyzed via Fisher's exact test. Data for other endpoints will be analyzed with Wilcoxon's test or analysis of covariance (ANCOVA) with baseline value as covariate. Full details of analysis methods, including how missing data will be handled, will be provided in the SAP which will be finalized prior to study unblinding.

11.3.3. PK Data

A listing of PK sample collection times as well as derived sampling time deviations will be provided. A subject listing of all concentration-time data for each treatment, and study day will be presented. PK variables will be summarized using appropriate descriptive statistics (e.g., n, mean, SD, CV%, minimum, median, and maximum, and/or geometric mean) by part, dose, and study day.

Graphical presentations of key PK parameters and concentrations will be used as appropriate. Figures of individual concentrations versus time will be presented by subject.

Steady state of GBT440 will be assessed graphically.

Exploration of exposure-response relationships of GBT440 to exploratory efficacy data, and safety data (described below) will be performed as data permits.

12. REGULATORY, ETHICAL AND LEGAL OBLIGATIONS

12.1. Ethical Consideration

It is the responsibility of the Investigator to assure that the study is conducted in accordance with current country and local regulations, FDA, ICH GCP, the Declaration of Helsinki, and Good Clinical Practice.

The study will be conducted according to the protocol, and guidelines established by the ICH for GCP in clinical trials.

12.2. Institutional Review Board (IRB) and Regulatory Approval

The Investigator must inform, and obtain approval from, the IRB/IEC for the conduct of the study at named sites, for the protocol, the Subject Informed Consent Form, and any other written information that will be provided to the subjects and any advertisements that will be used. Written approval must be obtained prior to recruitment of subjects into the study and shipment of investigational drug.

Proposed amendments to the protocol and aforementioned documents must be discussed between the Sponsor and CRO, and then submitted to the IRB/IEC for approval. Amendments may be implemented only after a copy of the local IRB approval letter has been transmitted to the Sponsor. Amendments that are intended to eliminate an apparent immediate hazard to subjects may be implemented prior to receiving Sponsor or IRB/IEC approval. However, in this case, approval must be obtained as soon as possible after implementation.

The Investigator will be responsible for ensuring that an annual update is sent to the IRB/IEC to facilitate their continuing review of the trial (if needed) and that the IRB/IEC is informed about the end of the study. Copies of the update, subsequent approvals and final letter must be sent to the Sponsor.

12.3. Insurance and Financial Disclosure

The Sponsor has subscribed to an insurance policy covering, in its terms and provisions, its legal liability for injuries caused to participating persons and arising out of this research performed strictly in accordance with the scientific protocol as well as with applicable law and professional standards.

Financial Disclosure statements will be handled in a separate agreement apart from the protocol, kept on file and submitted as applicable with any subsequent license application.

12.4. Essential Documentation Requirements

The Sponsor will collect from the investigational site the required essential regulatory documents per ICH guidance prior to GBT440 shipment to the site.

12.5. Informed Consent

It is the Investigator's responsibility to obtain written informed consent from the subject after adequate explanation of the objectives, methods, anticipated benefits, and potential hazards of the study and before any study procedures are commenced. The subject should be given a

copy of the Informed Consent Form (ICF) in their native language. The informed consent process should be recorded in the source documentation. The original copy of the signed and dated informed consent must be retained in the institution's records, and is subject to inspection by representatives of the Sponsor, or representatives from regulatory agencies.

12.6. Confidentiality

The Investigator must ensure that the subject's privacy is maintained. On the CRF or other documents submitted to the Sponsor, subjects will be identified by a subject study number only. Documents that are not submitted to the Sponsor (e.g., signed informed consent form) should be kept in a strictly confidential file by the Investigator.

The Investigator shall permit authorized representatives of the Sponsor, regulatory agencies and IRBs to review the portion of the subject's medical record that is directly related to the study. As part of the required content of informed consent, the subject must be informed that his/her records will be reviewed in this manner.

12.7. Trial Documentation and Data Storage

The Investigator must retain a comprehensive and centralized filing system of all trial-related documentation that is suitable for inspection by the Sponsor and representatives of regulatory authorities.

The Investigator must retain essential documents until at least 2 years after the last approval of a marketing application. Subject files and other source data (including copies of protocols, original reports of test results, investigational drug dispensing logs, correspondence, records of informed consent, and other documents pertaining to the conduct of the trial) must be kept for the maximum period of time permitted by the institution. Documents should be stored in such a way that they can be accessed/data retrieved at a later date. Consideration should be given to security and environmental risks.

No trial document will be destroyed without prior written agreement between the Sponsor and the Investigator. Should the Investigator wish to assign the trial records to another party or move them to another location, written agreement must be obtained from the Sponsor.

12.8. Study Record Retention

In accordance with 21 CFR 312.62(c), the investigators will retain records required to be maintained under this part for a period of 2 years following the date a marketing application is approved for the drug for the indication for which it is being investigated. If no application is to be filed or if the application is not approved for such indication, the investigator will retain these records until 2 years after the investigation is discontinued and the US FDA or applicable regulatory authorities are notified.

The investigators must retain protocols, amendments, IRB/IEC approvals, copies of the Form FDA 1572, signed and dated consent forms, medical records, eCRFs, drug accountability records, all correspondence and any other documents pertaining to the conduct of the study.

If the Principal Investigator moves, withdraws from an investigation or retires, the responsibility for maintaining the records may be transferred to another person who will accept responsibility. Notice of transfer must be made to and agreed by the Sponsor.

12.9. Disclosure of Information

Information concerning the study, patent applications, processes, scientific data or other pertinent information is confidential and remains the property of the Sponsor. The Investigator may use this information for the purposes of the study only.

It is understood by the Investigator that the Sponsor will use information developed in this clinical study in connection with the development of GBT440 and, therefore, may disclose it as required to other clinical investigators and to regulatory agencies. In order to allow the use of the information derived from this clinical study, the Investigator understands that he/she has an obligation to provide complete test results and all data developed during this study to the Sponsor.

Verbal or written discussion of results prior to study completion and full reporting should only be undertaken with written consent from the Sponsor.

12.9.1. Publication

The Sponsor intends to publish the results of the study as a whole once all subjects have completed the study and the study has been analyzed.

The Investigator may not submit the results of the study for publication without the prior consent of the Sponsor.

The Investigator or the Sponsor may not submit for publication or present the results of this study without allowing each of the other parties adequate time to review and comment on the pre-publication manuscript.

Authorship will be determined by mutual agreement and in line with the International Committee of Medical Journal Editors authorship requirements.

13. ADMINISTRATIVE OBLIGATIONS

13.1. Source Data

Original documents, data, records (e.g., clinic records, laboratory notes, memoranda, subject diaries or evaluation checklists, pharmacy dispensing records, recorded data from automated instruments, copies or transcriptions certified after verification as being accurate and complete, microfiches, photographic negatives, microfilm or magnetic media, X-rays, subject files, and records kept at the pharmacy, at the laboratories, and at medico-technical departments involved in the clinical trial) and all relevant sections of the subject's medical records and all other data collection made specific to this trial constitute source documents.

The completed CRF is not a source document. The Investigator/institution will permit trial-related monitoring, audits, IRB review and regulatory inspection by providing direct access to source documents.

13.2. Data Collection

The investigator will be responsible for maintaining accurate and adequate case records (source documents) from which data will be transcribed (or if electronically captured [EDC] source data, transferred) to CRFs designed to record data pertinent to this study. All relevant observations and data related to the study will be so recorded. This will include medical and medication history, physical examinations, a checklist of inclusion and exclusion criteria, investigational treatment administration, and a record of sample collection, clinical assessments, AEs, and final evaluation. The clinical site Clinical Research Associate (CRA) will review all CRFs and compare data to that contained in clinic notes and subjects' source documents/medical records.

Data collected for each subject will be entered into the CRF. The investigator will be responsible for the timeliness, completeness, and accuracy of the documentation entered into the CRFs.

13.3. Monitoring

It is understood that monitors, and any authorized personnel contracted to Sponsor may contact and visit the Investigator, and that they will be allowed to inspect the various records of the trial on request (CRFs and other pertinent data), provided that subject confidentiality is maintained, and that the monitoring is conducted in accordance with local regulations.

It is the monitor's responsibility to inspect the CRFs at regular intervals throughout the trial to verify adherence to the protocol, the completeness, accuracy and consistency of the data, and adherence to Good Clinical Practice guidelines.

The Investigator agrees to co-operate with the monitor to ensure that any problems detected during the course of these monitoring visits are resolved.

13.4. Quality Control and Quality Assurance

Quality Control will be performed according to the Sponsor or Sponsor's designee internal procedures. A Quality Assurance representative of the Sponsor may audit the study. All necessary data and documents will be made available for inspection.

15. APPENDICES

APPENDIX A SCHEDULE OF STUDY ASSESSMENTS

Study Day (Window)	Screening ^a		Treatment Period					Follow-up Visits	
	Day -21 to Day -1	Day 1	Day 2	Day 8 (+/- 2)	Day 15 (+/- 2)	Day 28 (+/- 2)	Day 29 (+3)	Day 45 ^b (+/- 3)	Day 58 (+/- 3)
Visit	1	2	3	4	5	6	7	8	9
Informed Consent ^c	X								
Eligibility Assessment	X	X							
Demographic data	X	X ^d							
Medical History and baseline conditions	X	X ^d							
Concomitant Medications	X	X	X	X	X	X	X	X	X
Complete Physical Examination ^e	X								X
Limited Physical Examination ^f		X		X	X	X	X	X	
Height	X								
Weight	X					X			
Vital Signs ^g	X	X	X	X	X	X	X	X	X
SpO ₂ ^h	X	X	X	X	X	X	X	X	X
ECG (12-lead) ⁱ	X			X	X	X		X	X
Adverse Events ^j	X ^j	X	X	X	X	X	X	X	X
Serum Pregnancy Test (females only) ^k	X								
Urine Pregnancy Test (females only) ^l				X	X	X		X	X
Hematology	X			X	X	X		X	X
Serum Chemistry	X			X	X	X		X	X
Urinalysis	X				X	X		X	X

Study Day (Window)	Screening ^a	Treatment Period						Follow-up Visits	
	Day -21 to Day -1	Day 1	Day 2	Day 8 (+/- 2)	Day 15 (+/- 2)	Day 28 (+/- 2)	Day 29 (+3)	Day 45 ^b (+/- 3)	Day 58 (+/- 3)
Coagulation Panel (PT, PTT, INR)	X					X			
Serum Erythropoietin	X					X		X	X
Serology (Hepatitis A, B, C, and HIV)	X								
PK Blood Samples ^m		X	X	X	X	X		X	X
Spirometry and DL _{CO}	X					X			X
6 Minute Walk Test ⁿ	X ⁿ				X	X			X
Cardiopulmonary Exercise Testing ⁿ			X				X		
Randomization (IxRS)		X							
Study Drug Dispensing to Subject ^o			X	X	X				
Study Drug Administration at site ^p		X	X	X	X	X			
St. George's Respiratory Questionnaire ^q		X				X			X
UCSD Shortness of Breath Questionnaire ^q		X		X	X	X		X	X
ATAQ-IPF Symptoms ^q		X		X	X	X		X	X
ATAQ-IPF Impacts ^q		X		X	X	X		X	X
End of Study Questionnaire ^f									X
Cough Visual Analogue Scale ^q		X		X	X	X		X	X

Abbreviations: ATAQ = A Tool to Assess Quality of Life; DL_{CO} = lung diffusing capacity measured using carbon monoxide; ECG = electrocardiogram; HIV = human immunodeficiency virus; INR = international normalized ratio; PK = pharmacokinetic; PRO = patient reported outcome; PT = prothrombin time; PTT = partial thromboplastin time; SGRQ = St. George's Respiratory Questionnaire; SpO₂ = oxygen saturation measured by pulse oximetry; UCSD = University of California San Diego.

Note: All assessments should be performed within the number of days (Window) as indicated for each scheduled visit day. All assessments should be performed prior to receiving study drug during the treatment period unless otherwise indicated. SGRQ, ATAQ, UCSD, Cough VAS should be performed before all other non-PRO assessments, followed by 12-lead ECG and then vital sign assessments.

CONFIDENTIAL

- a All screening evaluations must be completed and reviewed prior to Day 1 (Visit 2) to confirm the subject meets all eligibility criteria prior to randomization to the treatment period. In cases when the screening 6MWT is done more than 7 days prior to Visit 2, it must be repeated, up and through Day 1, prior to any Day 1 assessments.
- b All subjects who discontinue study or study drug prior to study completion and who are unwilling or unable to complete the remaining scheduled visits should return to the study site to complete all Day 45 (Visit 8) assessments (refer to [Section 6](#))
- c Written informed consent must be obtained and documented prior to performing any study-specific screening procedure
- d Demographics, medical history and baseline conditions obtained at screening should be reviewed again at this visit and any changes since screening updated in the eCRF
- e Includes evaluation of the head, eyes, ears, nose and throat and cardiovascular, respiratory, musculoskeletal, gastrointestinal, neurological, dermatologic systems. No rectal or pelvic examination is required. Record any observed abnormalities in the eCRF. At subsequent visits record new or worsened clinically significant findings on the eCRF
- f Perform a limited, symptom-directed examination as clinically indicated. Record new or worsened clinically significant findings in the eCRF.
- g Includes heart rate, respiratory rate, systolic and diastolic blood pressure and temperature measured whilst in a semi-recumbent or supine position and resting for at least 5 minutes.
- h Performed while the subject is seated and resting for at least 5 minutes.
- i Perform 12-lead ECG in triplicate; three separate tracings with approximately 1 minute between each tracing, after resting in a semi-recumbent or supine position for at least 5 minutes.
- j After informed consent but prior to randomization only serious adverse events (SAEs) resulting from a protocol-mandated intervention should be reported. After randomization, all adverse events will be reported until study completion (Day 58).
- k Performed for all female patients who are not post-menopausal or surgically sterile
- l If a urine pregnancy test is positive the result must be confirmed with a serum pregnancy test
- m PK blood samples during the treatment period should be collected on Days 1 and 28: Pre-dose and 2 hours post dose (+/- 15 minutes); Day 2: 24 hours (+/-2 hours) after the Day 1 dose *and* prior to receiving the Day 2 dose; Days 8 and 15: Pre-dose only.
- n Instructions for per-protocol performance of the 6-minute walk (and Borg dyspnea scale) and cardio-pulmonary exercise tests are provided in the procedure manual. Note: The baseline 6MWT performed during screening must be performed within 7 days of the Day 1 visit.
- o An unblinded study pharmacist will prepare daily doses of study drug, dispensed into 30 mL high-density polyethylene (HDPE) bottles. Each bottle (or dose) is packaged individually with 3 capsules of active or placebo or both specific to each subject's assigned treatment group. Subjects who have their dose modified during the study must return to the site to have the modified dose of study drug dispensed by the unblinded pharmacist.
- p Subjects should not administer study drug on the morning of these study visits. Study drug will be administered by the study staff after completion of all pre-dose assessments.
- q The SGRQ, ATAQ and UCSD questionnaires and cough VAS should be self-administered by the subject, using the paper forms provided by the Sponsor prior to all other non-PRO assessments and before the patient receives any disease-status information during that assessment. ATAQ questionnaires should be administered to subjects enrolled in Part B of the study.
- r The End of Study Questionnaire should be administered to subjects enrolled in Part B of the study.

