	
5. History of other medical conditions that are known or may result in interstitial lung disease. For example, any connective tissue disease including but not limited to scleroderma, polymyositis/dermatomyositis, systemic lupus erythematosus and rheumatoid arthritis.6. AST, ALT or total Bilirubin $>2 \times$ ULN.7. Creatinine Clearance (CrCl) <30 mL/min/1.73 m², calculated using the Modification of Diet in Renal Disease estimated Glomerular Filtration Rate (MDRD eGFR).8. Significant polycythemia defined as hemoglobin value >18 mg/dL.9. ECG with a QTcF >450 ms (males) or QTcF >470 ms (females). If ventricular pacing is noted on ECG, then QTcF intervals will not be calculated.10. Family or personal history of congenital long QT syndrome.11. Female who is breast-feeding or pregnant.12. Known current malignancy or current evaluation for a potential malignancy or history of malignancy within the past 2 years prior to screening, except for appropriately treated non-melanoma skin carcinoma, carcinoma in situ of the cervix, or Stage 1 uterine cancer.13. Subject has used any of the following therapies within 30 days of screening:
• Any cytotoxic, immunosuppressive or cytokine-modulating therapy including but not limited to: azathioprine, bosentan, ambrisentan, cyclophosphamide, cyclosporine, etanercept, iloprost, infliximab, leukotriene antagonists, methotrexate, mycophenolate, tacrolimus• Imatinib mesylate, interferon gamma-1b, tyrosine kinase inhibitors (excluding nintedanib)14. Pulmonary hypertension requiring active therapy including but not limited to endothelin receptor inhibitors or PDE inhibitors (e.g., sildenafil, tadalafil).
• Note: intermittent use of a PDE inhibitor for erectile dysfunction may be allowed after approval by the Medical Monitor.15. Hospitalization due to an exacerbation of IPF within 30 days of screening16. Subject plans to begin or has commenced pulmonary rehabilitation within 30 days of screening
• Subjects on a stable exercise regimen at screening or whose regimen, in the opinion of the investigator, is not expected to change at any time during the entire study will be considered eligible for the study17. Corticosteroids (>10 mg per day of prednisone or an equivalent) within 30 days of screening.
--	---

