1.5.3. Dose Rationale

The selection of GBT440 doses for investigation in IPF patients is based on pharmacodynamic (PD) targets that are expected to correspond to an increase in Hb-O₂ affinity which may result in a clinically significant increase in oxygenation. These PD targets are derived from data from three nonclinical pharmacology studies that included a hypoxia challenge model and two models of pulmonary hypoxemia (refer to the IB for details of these studies). Based on the in vivo data the lower limit for treatment response during exercise-induced desaturation is expected to be ~20% Hb occupancy by GBT440.

The dose levels predicted to achieve the Hb modification targets of ~20% to ~50% in IPF subjects are based on clinical PK and PD data from study GBT440-001. Dose levels of 600 mg or 900 mg per day administered to healthy subjects for 15 days resulted in a mean Hb modifications of 24% and 38%, respectively. A dose level of 300 mg per day resulted in a mean Hb modification of 11%, which is below the PD effect that showed benefit in animal models of hypoxemia.

The safety of the proposed doses of 600 mg and 900 mg in the initial cohort (Part A) of approximately 18 subjects and the safety of pursuing parallel dosing in this study are based on the totality of available nonclinical and clinical safety data. The expansion Cohort (Part B) of 15 subjects will have 3 dose arms: 1500 mg, 600 mg and placebo. Addition of a higher dose is supported by: the acceptable safety profile collected from the Part A subjects dosed to date in this study; review by the Safety Monitoring Committee of safety data from 12 subjects who completed up to 28 days and 16 subjects who completed 15 days of dosing in Part A and Safety Monitoring Committee agreement to proceed with the evaluation of GBT440 1500 mg; continued favorable safety profile in ongoing studies evaluating GBT440 in subjects with SCD, including continued dosing for up to 6 months; and an anticipated dose-dependent improvement in oxygen saturation. Guidelines for the safety review of Part A and Part B of the trial are outlined in the Safety Monitoring Committee section ([Section 10.1](#)).

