4. STUDY POPULATION

4.1. Inclusion Criteria

All subjects must meet the following inclusion criteria:

1. Able and willing to provide signed informed consent to participate in this study.
2. Documented diagnosis of IPF, as indicated in the ATS/ERS/JRS/ALAT 2011 guidelines.
3. Adult males or females aged 45–80 years inclusive at randomization.
4. Oxygen saturation (SpO₂) ≥88 % by pulse oximetry while breathing room air at rest.
5. Oxygen saturation (SpO₂) <88% and at least a 5% absolute decrease during the baseline 6MWT which is sustained for at least 10 seconds.
6. Able to walk a total of at least 100 meters at completion of the baseline 6MWT.
7. Weight ≥ 40 kg
8. Subject is seronegative for hepatitis A (IgM anti-HAV), hepatitis B surface antigen (HBsAg), hepatitis C antibody (anti-HCV), and human immunodeficiency virus antibody (anti-HIV) within 3 months of screening.
9. Able, in the Investigator's opinion, to complete the 6MWT unassisted at baseline and Day 15 and Day 28 and comply with the study procedures, including attending all assessment visits and adhering to all study requirements and restrictions.
10. Male or female of child bearing potential willing and able to use highly effective methods of contraception from study start to 3 months after the last dose of study drug.

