5.4.1.6. Other Clinical Laboratory Tests

Screening tests will include serology for hepatitis A (IgM anti-HAV), hepatitis B surface antigen (HBsAg), hepatitis C (HCV) and HIV-1/0/2 antibodies if there is no documented testing results within 3 months of screening.

For women of child bearing potential, a pregnancy test (serum HCG) will be performed at screening and urine pregnancy testing will be performed during the study. If the urine pregnancy test is positive the result must be confirmed with a serum pregnancy test.

Coagulation (Panel) including PT, PTT and INR will be collected at screening and Day 28.

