8.6. Fertility/Contraceptive Requirements

8.6.1. Acceptable Forms of Contraception

Highly effective methods of birth control are defined as those which result in a low failure rate (i.e. less than 1% per year) when used consistently and correctly.

- Combined (estrogen and progestogen containing) hormonal contraception associated with inhibition of ovulation:
 - Oral
 - Intravaginal
 - Transdermal
- Progestogen-only hormonal contraception associated with inhibition of ovulation:
 - Oral
 - Injectable
 - Implantable

Note: Hormonal contraception must be supplemented with a barrier method (preferably male condom).

- Intrauterine device (IUD)
- Intrauterine hormone-releasing system (IUS)
- Bilateral tubal occlusion
- Vasectomised partner. Note that vasectomised partner is a highly effective birth control method provided that partner is the sole sexual partner of the woman of child bearing potential trial participant and that the vasectomised partner has received medical assessment of the surgical success.
- Sexual abstinence. Sexual abstinence is considered a highly effective method only if the subject is refraining from heterosexual intercourse during the entire period of risk associated with the study treatments. The reliability of sexual abstinence needs to be evaluated in relation to the duration of the clinical trial and the preferred and usual lifestyle of the subject.

For male subjects:

- Men must agree to use two acceptable methods of contraception, at least one of which must be a barrier method (e.g., spermicidal gel plus condom) for the entire duration of the study, and for 3 months following last study drug administration.

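### Minor safety improvement: the only pregnancy test before first dose is the Screening serum test, so a Day 1 urine test would be a cheap second check

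*Protocol*

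**What the plan says.** Exclusion criterion 11 (Protocol 4.2) bars entry for a "Female who is breast-feeding or pregnant". On testing, Protocol 5.4.1.6 says that for women of child-bearing potential "a pregnancy test (serum HCG) will be performed at screening and urine pregnancy testing will be performed during the study". It names no days.

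Appendix A supplies them. The serum row is marked at Screening only. The row "Urine Pregnancy Test (females only" is marked on Days 8, 15, 28, 45 and 58. The table in SAP 5.1 is the same. Day 1 carries the second eligibility assessment, the IxRS randomisation and the first dose at site, and its cell is empty in both pregnancy rows. The footnotes add no re-test. Footnote k limits testing to women who could become pregnant, and footnote l requires serum confirmation of a positive urine result.

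The only other Day 1 check that bears on this is footnote d: demographics, "medical history and baseline conditions obtained at screening should be reviewed again at this visit". It does not name pregnancy.

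The main preventive safeguard is inclusion criterion 10 (Protocol 4.1), which requires subjects to be "willing and able to use highly effective methods of contraception from study start to 3 months after the last dose of study drug". Protocol 8.6.1 sets the standard at a failure rate below 1% per year and adds that "Hormonal contraception must be supplemented with a barrier method". Protocol 6.3 and 10.9 require study drug to be stopped, and the pregnancy reported and followed, if one occurs.

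**The concern.** The eligibility decision that matters is made on Day 1, just before an investigational drug is given, but the pregnancy result behind it may be up to three weeks old. Contraception from study start does not cover a conception shortly before screening, which a serum test taken too early could miss. The stopping and reporting rules act only after exposure.

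The protocol accepts elsewhere that a screening result can go stale: a 6-minute walk test done more than 7 days before Day 1 must be repeated (Protocol 5.1; Appendix A, footnote a). The pregnancy test has no matching rule.

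What is at stake is participant and fetal safety alone. Protocol 5.2 states that nothing is known about effects on the human fetus, and reproductive toxicity details are left to the Investigator's Brochure (Protocol 1.4.5). Pregnancy results are only listed (SAP 15.2.4), so no estimate or comparison is touched.

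**Working it through.** The plan gives no figure of its own here, so the check is a count of days and doses.

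**Age of the result at first dose.** Inputs: Screening window Day -21 to Day -1; randomisation and first dose on Day 1 (Appendix A). There is no Day 0, so Day -21 to Day 1 is 21 days and Day -1 to Day 1 is 1 day. Range: 1 to 21 days.

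**Usual age.** The baseline walk test must fall within 7 days of Day 1 or be repeated (Protocol 5.1, 5.5.3). If the serum sample is taken at the same visit as a valid walk test, the result is at most 7 days old. It is older if the walk test is repeated later, as the protocol permits, or if screening is spread over several days.

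**Doses before the next test.** Dosing is daily from Day 1, and on visit days it follows the assessments (Protocol 8.1). Doses before the test are therefore the visit day minus 1:
- Day 8 nominal: 8 - 1 = 7 doses
- Day 6 (window -2): 6 - 1 = 5 doses
- Day 10 (window +2): 10 - 1 = 9 doses

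**Effect of a Day 1 test.** Time from last test to first dose falls from 1-21 days to 0. The longest gap between tests at this stage falls from 30 days (Day -21 to Day 10) to 21 days (Day -21 to Day 1).

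**Why the gap narrows but does not close.** A very recent conception is undetectable. Let w be that period, assumed to be 7 to 14 days and equal for serum and urine (the documents give no value), and g the days from the serum test to Day 1. Conceptions missed by the serum test fall within g + w days before Day 1, and a Day 1 test catches g of those days. Share caught = g/(g + w):
- g = 21: 21/35 to 21/28 = 60% to 75%
- g = 7: 7/21 to 7/14 = 33% to 50%
- g = 1: 1/15 to 1/8 = 7% to 13%

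The benefit sits mainly in long screening intervals, which is where a 7-day trigger would act.

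**Order of magnitude, illustration only.** Part B has up to 15 subjects, 9 + 3 = 12 of them on active drug. Assume 0 to 3 eligible women among 33. The upper end on active drug in Part B is 3 x 15/33 x 12/15 = 1.09. Conceptions in a 21-day gap at the 1% per year contraception ceiling: 1.09 x 0.01 x 21/365 = 0.0006. Conceptions just before screening, at an assumed upper rate of 10% per year over 14 days: 1.09 x 0.10 x 14/365 = 0.0042. The upper total is about 0.005 exposed conceptions and the lower end is 0. Most of the upper figure comes from the two inputs with no source in the documents.

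**The case against.** The strongest case against is that this is a preference for one more test. No rule in either document requires a Day 1 test, ECG, hematology and chemistry follow the same Screening-then-Day-8 pattern, and the population is aged 45 to 80 with a disease commoner in men (Protocol 1.1, 4.1). All of that stands, and it is why the point is minor and not an error. It does not remove the point: Day 1 is an existing visit, the test is already used at five later ones, and the tested group need not be empty, since entry starts at 45 and menopause is defined by at least 2 years of amenorrhoea (Protocol 5.2).

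Three stronger readings are tempting, and the documents do not support them.
- A reader might infer that no pregnancy test guards the first dose. The Screening serum test does so, and footnote a requires screening results to be reviewed before Day 1. A Day 1 test would be a second check.
- A reader might take 21 days as the usual age of the result. It is the worst case, for the walk-test reason given above.
- A reader might treat the illustrative exposure count as an estimate. The number of eligible women, the pre-screening conception rate and the undetectable period are all assumed, and the fetal hazard cannot be judged without the Investigator's Brochure.

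**Conclusion.** The point holds as a minor safety improvement. Firm from the documents: one pre-dose pregnancy test, 1 to 21 days old at first dose, and 7 doses (5 to 9) before the next. The expected benefit of a Day 1 test is very small and may be zero, and the documents do not allow it to be quantified.

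A change would act mainly in Part B. The schedule is the same in both parts, but this version of the protocol already reports "16 subjects who completed 15 days of dosing in Part A" (Protocol 1.5.3), out of about 18. No endpoint, analysis population or safety summary is affected.

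**What to change.** Add a Day 1 mark to the urine pregnancy test row in Appendix A and in SAP 5.1, for women who are neither post-menopausal nor surgically sterile. Require the result to be read before IxRS randomisation and first dose, and confirm a positive by serum test under footnote l. The minimum version requires the Day 1 test only when the serum result is more than 7 days old, matching the walk-test repeat rule.

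The cost per subject is one urine test at an existing visit, for very few women and possibly none, with a possible delay to randomisation after a false positive. There is no new visit or analysis, and no routine extra blood draw. The administrative cost is larger: under Protocol 12.2, "Amendments may be implemented only after a copy of the local IRB approval letter has been transmitted to the Sponsor", and about 10 to 15 sites are planned. A stand-alone amendment would be out of proportion, so make the edit with the next amendment needed for another reason.
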